Patient Aligned Care Team (PACT) Intensive Management (PIM) Project Protocol

Modified 1-29-2020

Contents

Background	2
Summary of outcome measures	2
Primary and Secondary Outcome Measures Procedures	4
Sample selection and recruitment	4
Demonstration Site Selection:	4
Inclusion criteria:	4
Exclusion criteria:	5
Sample	5
Interventions	6
Measurements	6
Analysis	6
Other Outcome Measures	7
Functional Status, Quality of life, Symptom Burden	7
Implementation Outcome/challenges	7
Sample selection/ recruitment	7
Instrument Development	8
Procedures	8
Analysis	8
Primary Care Staff Job Satisfaction and Intention to Stay at the VA	8
Sample	8
Method	8
Analysis	9

Background

In 2013, VHA Primary Care Services submitted a request for proposal (RFP) seeking VA Medical Center (VAMC) participation in a national PACT Intensive Management (PIM) initiative. The specific objectives of the initiative were to 1) reduce preventable hospitalizations and emergency care in persons having complex medical and social needs and who are identified as being at highest risk for unplanned visits, hospitalization, and death, 2) optimize high-risk patient functional status, and 3) maintain high-risk patients in their homes and communities to the greatest extent possible. Through the RFP, five VAMCs were selected to receive funding for up to \$750,000 per year to support demonstration projects to innovate strategies to manage high-risk Veterans in a rigorously evaluated quality improvement project. Through this initiative, the PIM teams at each of the demonstration sites became subject matter experts and valuable advocates for high-risk patients' individual and system-level needs.

Summary of outcome measures

Primary Outcome Measure:

1. VA health care cost
Total costs of VA care, including inpatient, outpatient, pharmacy and fee-basis services.

Secondary Outcome Measures:

2. Healthcare Utilization

VA central repository administrative data will be analyzed to calculate utilization of hospital, emergency and outpatient primary and specialty care. This information will be electronically abstracted through the VA central repository administrative data center.

3. Medicare utilization and cost

Medicare claims data was used to capture utilization and costs for services reimbursed by Medicare. The Master Beneficiary Summary File was used to ascertain patients' Medicare enrollment status.

Other Pre-Specified Outcome Measures:

4. Engagement

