The investigators will survey Primary Care Providers (PCPs) (physicians, MDs/DOs; nurse practitioners, NPs; physician assistants, PAs) and nurses (registered nurses, RNs; licensed practical nurses, LPNs; licensed vocational nurses-LVNs) at the five healthcare systems that have a PIM team. They will use both online using RedCap and paper-and-pencil versions of the survey to increase response rate. The investigators will survey Primary Care staff at baseline and one year later. The first survey was fielded December 2014 - May 2015 and again from October 2016 - January 2017). Intention to Stay at the VA is measured by a single item "I intend to continue working in PC at the VA for the next two years," rated on a 5-point Likert agreement scale.

Primary and Secondary Outcome Measures Procedures

Sample selection and recruitment

Demonstration Site Selection: Five sites will be selected in a competitive process by reviewers and funders from the VHA Office of Primary Care Services. Selection criteria include sites that: 1) have geographically diverse teams, spanning both rural and urban settings; 2) have teams that include a mental health provider; and 3) provide services that can increase Veteran access to healthcare, including home visits and telehealth.

Inclusion criteria: The evaluation team will collaborate with demonstration sites over six months to define and identify the high-risk Veteran population using the CAN score (Wang et al.) The CAN score is computed weekly for each VHA patient based on multiple electronic data elements (i.e., clinical diagnoses, laboratory data, vital signs, previous inpatient and outpatient utilization over the preceding year) and predicts risk of hospitalization in the subsequent 90 days. The patient lists will include those on the top 10th percentile of the CAN score and that had at least one ED visit or hospitalization in the VHA over the prior 6 months. All patients will have an assigned primary care medical homes in general Primary Care, Women's Health, Geriatrics, or Infectious Disease (mostly caring for patients with Human Immunodeficiency Virus, HIV). The Infectious Disease medical home will be included as a tracer for assessing specialty medical homes, to provide formative information on differences from primary care medical homes.

Table 1. Exclusion Criteria

Exclusion Criteria

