Patient demographics, chronic conditions and other health conditions (Yoon, Scott, Phibbs, & Wagner, 2011), comorbidity score (Charlson), VHA outpatient/inpatient utilization, measures of prescription drug use and mortality will be obtained through the VHA Corporate Data Warehouse. For costs, VHA inpatient and outpatient utilization records will be linked to Managerial Cost Accounting (MCA) cost data to obtain the costs of outpatient and inpatient care. Pharmacy utilization and costs will be obtained from MCA Pharmacy files, and VHA-sponsored care is obtained from Fee Basis files. Implementation costs will be determined through micro-costing methods from site reports. Because these are administrative data, these are collected from each participant regardless if they were not offered services or if they were discontinued from the intervention.

Analysis

The investigators will conduct an intent-to-treat analysis based on patients' allocated group. The investigators plan to compare unadjusted mean utilization counts and costs for different categories of inpatient care and outpatient care and total care. The investigators will estimate the impact of PIM using regression models to obtain the differences-in-differences estimate of the change from the 12-month pre-intervention period to 12-month and 24-month post-intervention period attributable to PIM above and beyond any time trends that occurred in both groups. Our regression models will predict utilization of outpatient encounters and inpatients stays in count data models (Poisson and negative binomial regression models) including a time-varying measure of risk using the Charlson Index and patient fixed effects to account for factors fixed over time. Regression models of costs include the same predictors as the utilization models and will be conducted using ordinary least squares (OLS); sensitivity analyses will be conducted using generalized linear models (GLM) with a log link and Poisson distribution. Mortality will be compared between treatment groups with a log-rank test for equality of survivor functions.

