In other sensitivity analyses, the investigators plan to conduct regression models with patient random effects and covariates for patients' age, gender, race/ethnicity, marital status, means test, service connection, homelessness, Charlson Index, and site. The investigators will also measure the treatment effect on the treated by conducting regression analysis using instrumental variables to examine whether more PIM encounters were related to cost and utilization impacts by using randomization to PIM as an instrument for number of PIM encounters. Instrumental Variable models will use the two-staged least squares estimator.

Other Outcome Measures

Functional Status, Quality of life, Symptom Burden

Standardized assessments of symptom burden (mental health and physical health), quality of life, and functional status (physical, social, and mental) will be based on patient-reported outcomes measurement information system (PROMIS) global items. These measures will be obtained only on the innovation patients and entered into the electronic medical record using a standardized assessment template available only to the demonstration staff. Some standardized assessments are available on the entire sample as part of VHA medical records (i.e., pain score, Patient Health Questionnaire (PHQ)-2 for depression) and performance measures.

Implementation Outcome/challenges

Sample selection/ recruitment

The investigators will interview PIM staff about implementation challenges and lessons. The investigators will use PIM staffing lists from the demonstration sites to compile the sampling frame. The investigators will include in the sampling frame the team leaders, team members, and program coordinators. The investigators will select all PIM team leads and program coordinators (if the site has a coordinator), and randomly select 1 of each job title/role from the PIM team members. Team members who refuse or are ineligible will be replaced by randomly selecting another person in the same job title/role, until one completed interview is obtained for each job title/role for each site. Team members will include RNs, NPs, MDs, social workers, psychologists, and intermediate care technicians. The investigators will invite 35 potential respondents by email, and follow up by telephone and using instant messaging for those who do not respond to the initial email.

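### The models that estimate the PIM effect on cost and utilisation adjust for Charlson change recorded after randomisation, so they may not give the total intent-to-treat effect

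*Protocol*

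**What the plan says.** All references are to the Protocol; no SAP is at hand. The Analysis section under Primary and Secondary Outcome Measures Procedures opens: "The investigators will conduct an intent-to-treat analysis based on" the allocated group. It assigns the impact of PIM to regression-based difference-in-differences, from the 12 months before the intervention to 12 and 24 months after it. The utilisation models are Poisson or negative binomial, "including a time-varying measure of risk using the Charlson Index and patient fixed effects to account for factors fixed over time". For cost, the primary outcome, it says: "Regression models of costs include the same predictors as the utilization models", fitted by OLS.

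The Charlson score comes from administrative records. Under Measurements: "comorbidity score (Charlson), VHA outpatient/inpatient utilization, measures of prescription drug use and mortality will be obtained through the VHA Corporate Data Warehouse". No look-back window is given.

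Two further analyses bear on the point. The section says: "The investigators plan to compare unadjusted mean utilization counts and costs". A random-effects sensitivity model has a covariate list ending "service connection, homelessness, Charlson Index, and site", without saying whether that Charlson value is the baseline one. No regression is described that omits Charlson or restricts it to its pre-allocation value.

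**The concern.** A patient fixed effect absorbs everything constant about a patient, including the average Charlson level. What remains of a time-varying Charlson term is change within the patient, and that change includes values recorded after randomisation. It is therefore a possible consequence of allocation, not a baseline characteristic.

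The Protocol gives reasons to expect that PIM could move it, in either direction. Sites are chosen partly because they "provide services that can increase Veteran access to healthcare, including home visits and telehealth", and more contacts can produce more recorded diagnoses. The initiative also aims to "reduce preventable hospitalizations and emergency care in persons having complex medical and social needs". Fewer admissions mean fewer occasions for coding, and better health means less morbidity to code.

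Holding Charlson change constant then has one of two effects. If PIM only adds codes, its patients look sicker than they are and PIM appears to save money. If PIM truly reduces morbidity, the saving that runs through that reduction is adjusted away. Because patients are randomised, baseline risk is balanced in expectation and the term is not needed to remove confounding.

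**Working it through.** **The plan's own figure.** For d = 0.2, two-sided alpha 0.05 and 90% power, n = 2(1.960 + 1.282)²/0.2² = 525.4, so 526 per arm, as the Protocol states. This concern does not change it. The planned recruitment is 1000 per arm, which is used below.

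**Identity.** With one pre and one post period, the fixed-effects model is OLS on the change scores, and

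adjusted effect = total effect − b × delta,

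where b is the fitted within-patient cost slope per Charlson point and delta is the arm-average Charlson shift caused by PIM, diluted by allocated patients who are never served.

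**Range.** Neither b nor delta is in the documents. Assume b = 0.05 to 0.3 SD per point and delta = −0.2 to +0.2 points:

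- delta = +0.2, b = 0.3: error −0.06 SD
- delta = −0.2, b = 0.3: error +0.06 SD
- delta = 0: error 0

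**Scale.** With equal variances and pre–post correlation rho, SE = √[2(1 − rho) × 2/1000]. A bias of 0.652 SE raises the two-sided type I error from 5% to 10%. The midpoint column uses b = 0.175 and |delta| = 0.1, a bias of 0.0175 SD. The extreme column uses 0.06 SD.

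| rho | SE (SD units) | Bias giving 10% | Type I error, midpoint | Type I error, extreme |
|---|---|---|---|---|
| 0.3 | 0.053 | 0.0345 | 6.3% | 21% |
| 0.5 | 0.045 | 0.029 | 6.8% | 27% |
| 0.7 | 0.035 | 0.023 | 8.0% | 41% |

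**Simulated cost model.** Change-score OLS, 1000 per arm, rho 0.5, b = 0.2, SD of natural Charlson change 1, 1500 replicates; all inputs are assumed. Mean estimates in SD units:

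| Scenario | True total effect | With Charlson | Without Charlson | Unadjusted post means |
|---|---|---|---|---|
| Extra coding only, delta +0.2 | 0 | −0.038 | 0.002 | 0.003 |
| Fewer codes only, delta −0.2 | 0 | +0.040 | −0.001 | −0.001 |
| Real morbidity gain, delta −0.2 | −0.040 | −0.001 | −0.041 | −0.040 |
| Larger effect, −0.04 of it through morbidity | −0.20 | −0.160 | −0.199 | −0.200 |
| No shift | 0 | −0.001 | −0.001 | 0.000 |

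A separate simulation (1000 per arm, 600 replicates, units of the residual SD of the cost change) added an unmeasured factor driving both Charlson change and cost. With true effect 0, delta = +0.2 and slopes of 0.1 and 0.3, the adjusted estimate moved to −0.079 and −0.113, with rejection rates of 36% and 63%. Without that factor the estimates were −0.020 and −0.060, with rejection rates of 7.5% and 27.5%.

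**Count models.** With an assumed rate ratio of 1.2 per Charlson point, delta = +0.2 multiplies the PIM rate ratio by 1.2^(−0.2) = 0.96, and delta = −0.2 by 1.2^(0.2) = 1.04. A two-period Poisson fixed-effects simulation agreed. Under extra coding with a true ratio of 1.00, it gave 0.965 with Charlson and 1.001 without.

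**The case against.** The strongest reply is that the harm rests on an undocumented premise: nothing in the Protocol shows that allocation shifts recorded Charlson. The cohort is in the top tenth of predicted risk with a recent ED visit or admission, so it is probably well coded already. Many allocated patients may never be served; if half are, a 0.2-point arm average needs 0.4 points among those served (0.2/0.5). Over the assumed range, weighted uniformly, type I error reaches 10% in only 13%, 20% and 31% of cases at rho 0.3, 0.5 and 0.7. All of this stands. It limits the likely size but does not make the term harmless, because the sign is unknown.

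The planned unadjusted means are free of this bias and recover the truth in every cost scenario above. That also stands. However, the Protocol names the regression, not the means, as the estimate of PIM's impact.

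The look-back window may be set in the SAP. A lagged window would protect the first 12 months, and also a 24-month window treated as one cumulative period. It would not protect months 13 to 24 modelled as a separate period. The Charlson term in the random-effects model may already be the baseline value, so that model is ambiguous and does not confirm the fault.

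Finally, the Protocol defines intent-to-treat by allocated group and does not use the term total effect. That is fair, but an impact estimate for randomised groups is ordinarily read as the effect of allocation.

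**Conclusion.** The concern holds. The Protocol itself fixes Charlson as time-varying in the models for the primary cost outcome and for utilisation, so this is not a detail left open for the SAP. Those models may not estimate the total effect of allocation. On the assumed slopes and shifts the error is at most 0.06 SD in either direction, or 30% of the 0.2 SD design effect (0.06/0.2). It is 0.0175 SD at the middle of the range and zero if PIM leaves recorded Charlson unchanged. An unmeasured common cause of Charlson change and cost can make it larger. The algebra is certain; the size in this trial cannot be known from the documents. It is best treated as a cheap improvement that removes an avoidable bias of unknown sign from the primary estimate.

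**What to change.** In the main cost model and the count models, at both 12 and 24 months, keep patient fixed effects, period and allocated arm × period, and drop Charlson. Possible wording: *Models include patient fixed effects, period and allocated arm by period; no covariate measured after allocation is included.*

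Outside the fixed-effects model, use only pre-allocation covariates (pre-period cost or utilisation, baseline Charlson, site, gender), and state that Charlson in the random-effects model is the baseline value. Keep the time-varying Charlson model as a labelled sensitivity analysis, give its look-back window, and report mean recorded Charlson change by arm so that readers can see delta.

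Regressing post-period cost on arm and pre-period cost may be more precise, but that is an optional efficiency choice and not part of the correction.

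No new data are needed. On the assumed inputs, omitting Charlson changed the SE by about 1–2% (for example 0.0446 against 0.0441 SD). The real cost is one of timing. The Protocol was modified in January 2020, so if outcome data have already been seen, the change must be declared post hoc and shown beside the estimate from the planned model.

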
• A clinical encounter with specialty primary care teams with comprehensive resources other than those identified in inclusion criteria (i.e., Post-Deployment, Renal, Spinal

Cord Injury, Homeless PACT, Home-Based Primary Care team), in the previous two months

- Outpatient encounters in Mental Health Intensive Care Management programs (VHA-adapted Assertive Community Treatment program), palliative care, and hospice in the previous two months
- Nursing home in the previous two months
- Care Assessment Need Score (CAN) (Wang et al.) < 90th percentile
- Inpatient admission to a residential substance abuse treatment program in the previous two months
- Death

Exclusion criteria: Patients will be excluded if they are managed by an intensive primary care team or have received intensive outpatient services in the past two months, such as homeless primary care services, primary care for home-bound patients, intensive outpatient mental health services. Patients residing in a VHA nursing home facility or residential substance abuse treatment program in the previous two months will also be excluded. Full exclusion criteria are listed in Table 1.

Sample: The evaluation team will randomly identify a sample of high-risk Veterans from among patients assigned to a primary care medical home at a demonstration site. Half of these patients will be randomly allocated to the innovation group and sent to the demonstration teams for recruitment consideration, and the other half will be allocated to usual care in the VA patient-centered medical home. The investigators will stratify by gender to ensure representation of 10% women in both the innovation group and the usual care group to inform future policy. Demonstration teams will receive lists of high-risk patients from the evaluation team through a secure workspace behind VHA firewall. Demonstration patients on this list are considered innovation patients (intent-to-treat), if they receive services from the demonstration teams. Demonstration teams will be blinded to the list of usual care patients in the comparison group as part of the quality improvement design.

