The investigators will use both online using RedCap and paper-and-pen versions of the survey to increase response rate. The investigators will survey Primary Care staff at baseline and one year later. The first survey will be fielded December 2014 - May 2015 and again from October 2016 - January 2017).

Analysis

Longitudinal cohort of staff who responds to both Wave 1 and Wave 2. The investigators will use ordinary least squares regression analysis to examine associations between the independent variable measured at wave 1 and outcome variables measured at wave 2 controlling for wave 1 outcomes among staff who completed both waves. The investigators will focus on Job Satisfaction and Intention to Stay at VA as dependent variables. The investigator will adjust for provider-level covariates (type of staff, location, type of primary care team, gender, length of time at VA) and clustering of respondents within clinics assuming a random effect using robust standard errors. The investigators will use sample weighting for nonresponse based on provider characteristics in both waves and conduct multiple imputations for item-level missing data;

Difference-in-differences between Wave 1 and Wave 2: will treat Wave 1 and Wave 2 as two independent samples and use difference-in-difference regression analysis to assess differences in outcome variables between Wave 1 and Wave 2 among PIM and usual care. The investigators will focus on primary care staff experience (e.g., stress, satisfaction with help received) working with high-risk patients as dependent variables. The investigators will adjust for covariates (type of staff, location, type of primary care team, gender, length of time at VA). The investigators will use sample weighting for nonresponse based on provider characteristics in both waves.

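### The mortality log-rank test uses neither the allocation factors nor the baseline CAN score; it is valid, but a stratified test plus an adjusted Cox model would be a small free improvement

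*Protocol*

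**What the plan says.** The mortality analysis stands in the Protocol under Primary and Secondary Outcome Measures Procedures, Analysis: "Mortality will be compared between treatment groups with a log-rank test for equality of survivor functions". Nothing is said there about strata, covariates or an effect estimate.

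The design supplies three baseline variables that such an analysis could use:

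- **Gender.** Under Sample: "The investigators will stratify by gender to ensure representation of 10% women in both the innovation group and the usual care group".
- **Site.** The same section says that the evaluation team will "randomly identify a sample of high-risk Veterans from among patients assigned to a primary care medical home at a demonstration site", and then: "Half of these patients will be randomly allocated to the innovation group and sent to the demonstration teams for recruitment consideration". Site is not named as a stratum, but allocation within site is the natural reading.
- **CAN score.** Under Inclusion criteria: "The CAN score is computed weekly for each VHA patient based on multiple electronic data elements". Eligibility depends on it, so everyone selected has a value. The text says that it "predicts risk of hospitalization in the subsequent 90 days". The title of the paper cited for it is "Predicting risk of hospitalization or death among patients receiving primary care in the Veterans Health Administration".

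The cost and utilization models do account for fixed patient characteristics, through patient fixed effects. Sensitivity models add a covariate list that includes gender and site. Neither is stated to cover mortality, which is also absent from the ten numbered outcomes in the Summary of outcome measures.

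**The concern.** A plain log-rank test treats everyone at risk at a given death time as having the same underlying hazard. If hazards differ between patients, those at high risk die first, and they do so faster in the arm with the higher death rate. The arms' risk sets then drift apart in composition and the observed contrast shrinks towards no effect. Comparing like with like, by strata or covariates, recovers some of that sensitivity.

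Two things are at stake. One is some power to see a mortality difference. That matters here because patients who die stop accruing VA cost, so a difference in deaths bears on how the primary cost outcome is read. The other is that a log-rank test alone gives a p-value without a hazard ratio or confidence interval, so a non-significant result would not show how large a difference remains compatible with the data.

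**Working it through.** **The Protocol's own figure.** The sample size is for ED visits or hospitalizations, not mortality. With d = 0.2, two-sided alpha 0.05 and 90% power, n per arm = 2(1.960 + 1.282)² / 0.2² = 525.4, rounded up to 526. The stated 526 per arm is reproduced. No death rate, hazard ratio or power is given for mortality.

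**Inputs from the Protocol.** 1,000 per arm; five sites with about 200 per arm each; 10% women; 1:1 allocation; two-sided 0.05 (stated for the other outcomes). The 24-month horizon is stated for cost and utilization and is assumed to apply to mortality.

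**Assumed inputs.** Control mortality over the horizon 10% to 30%; treatment hazard ratio (HR) 0.75 or 0.80; CAN HR per standard deviation 1.2, 1.5 or 2.0; site standard deviation on the log hazard 0.2 (0.4 in the CAN 2.0 scenarios); women versus men HR 0.6.

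**Baseline power of the plain test.** Expected deaths D = 1000m + 1000[1 − (1 − m)^HR], with m the control mortality. Power = Φ(|ln HR|·√(D/4) − 1.96). At HR 0.75:

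- m = 10%: D = 176; 0.2877 × √44 = 1.908; power Φ(−0.05) = 48%.
- m = 20%: D = 354; 0.2877 × √88.5 = 2.706; power Φ(0.75) = 77%.
- m = 30%: D = 535; power 91%.

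There is room for improvement unless deaths are frequent.

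**Simulation.** 1,500 trials per scenario, allocation balanced within site by gender, all three tests run on the same simulated data. Power in percent:

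| Mortality, HR | CAN HR per SD | Plain log-rank | Stratified by site × gender | Cox: CAN, gender, site | Gain, stratified | Gain, Cox |
|---|---|---|---|---|---|---|
| 10%, 0.75 | 1.2 | 47.9 | 47.9 | 47.9 | 0.0 | 0.0 |
| 10%, 0.75 | 1.5 | 46.3 | 46.3 | 46.7 | 0.0 | 0.4 |
| 10%, 0.75 | 2.0 | 44.1 | 44.5 | 47.0 | 0.4 | 2.9 |
| 20%, 0.75 | 1.2 | 77.0 | 77.3 | 77.9 | 0.3 | 0.9 |
| 20%, 0.75 | 1.5 | 74.3 | 74.8 | 75.9 | 0.5 | 1.6 |
| 20%, 0.75 | 2.0 | 70.1 | 70.9 | 75.1 | 0.8 | 5.0 |
| 30%, 0.80 | 1.2 | 71.7 | 72.4 | 72.3 | 0.7 | 0.6 |
| 30%, 0.80 | 1.5 | 73.5 | 74.3 | 76.2 | 0.8 | 2.7 |
| 30%, 0.80 | 2.0 | 64.2 | 65.8 | 74.6 | 1.6 | 10.4 |

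The Monte Carlo standard error of a single power figure is at most √(0.25/1500) = 1.3 points. Because the tests share the same simulated trials, the gains are more stable than that.

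**Validity.** Under no treatment effect (20% mortality, CAN HR 1.5), the rejection rates were 4.3%, 4.3% and 4.1%. With a standard error of √(0.05 × 0.95/1500) = 0.56 points, all are compatible with 5% and the tests do not differ from one another.

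**Size of strata.** Site × gender gives 10 strata, and 200 women over five sites is 40 per female stratum. Adding CAN quintiles gives 5 × 2 × 5 = 50 strata, and 200/25 = 8 women per female stratum.

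**The case against.** The strongest reply is that nothing here is in error. The Protocol names a valid test and is silent on strata, which a statistical analysis plan not shown may settle. Mortality is not a listed outcome and has no power target. The contrast with the cost models is no inconsistency either: patient fixed effects need a pre-period, and death has none. All of this stands, and it keeps the point minor. It does not remove it, because the Protocol does prescribe a formal mortality test and a better form is available from data already held.

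The reply also limits the size. Site is only implied as an allocation factor, and site and gender together add very little. The useful gain depends on how strongly CAN predicts death within a sample cut to the top decile, and the Protocol gives no figure for that. Its text speaks of hospitalization; death appears only in the cited title.

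A reader might infer two stronger things. The first is that the unstratified test is conservative or otherwise wrong; the null simulation shows no such difference. The second is that the trial forgoes a lot of power by ignoring its allocation factors; the gain from those factors never exceeded 1.6 points.

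**Conclusion.** The point holds as a minor efficiency improvement. The planned log-rank test is valid. Using gender and site gains about 0 to 1.6 power points. Adding the CAN score through a Cox model brings the gain to about 0 to 3 points if the CAN hazard ratio per standard deviation is 1.2 to 1.5, and to about 3 to 10 points if it is 2.0. The upper end also needs about 30% mortality, and those CAN 2.0 scenarios assume larger site differences as well.

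These ranges rest wholly on assumed death rates, treatment effects and prognostic strengths. The direction is secure: the Cox model never had lower power than the plain test in any scenario tried. The hazard ratio and confidence interval are worth having even if the power gain is nil.

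**What to change.** Amend the one sentence on mortality in the Analysis section:

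- Keep the log-rank test, stratified by gender and site only.
- Add a Cox model with treatment, baseline CAN score as a continuous covariate, gender and site. Report the hazard ratio with its 95% confidence interval, described as conditional on those covariates.
- Take the CAN score held at allocation. It is recomputed weekly, and later values could be affected by the intervention.
- Say in advance which of the two analyses carries the inference, so that there is only one mortality test. If it is the stratified log-rank test, the gain from CAN shows only in the Cox estimate.

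Do not stratify by site, gender and CAN quintile together, because the female strata would be too thin. Entering CAN as a covariate avoids that.

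The cost is a few lines of analysis. CAN, gender, site and mortality are all in administrative data already held for both arms, and neither the sample size nor the conduct of the trial changes.
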